4.1 Design/Randomization

This study has two components. Initially, subjects will receive ISIS 304801 or placebo, in a 1:1 randomized, double-blinded fashion for 16 weeks. Randomization will occur after verification that all eligibility criteria have been met. The randomization will be stratified by use of lipid-lowering medications. After completion of 16 weeks, all subjects will receive ISIS 304801 for 12 months in an open-label extension (OLE) phase. After discontinuation of ISIS 304801 (due to study end or any other reason) subjects will be followed for an additional 12 week withdrawal phase when possible. Patients who experience benefit (triglyceride lowering $\geq 50\%$) may receive an additional 12 months of open label drug (up to 24 months, total). This period may initiate immediately following the standard 12 month OLE, or following the withdrawal phase.

- 1° outcome (Δ in log₁₀ triglycerides):
 - C vs D
 - F vs G
- 2°/3° outcomes – within subject comparisons:
 - C vs E
 - F vs H
- Placebo vs drug comparisons
 - C vs H

1

4.2 Outcome Measures

4.2.1 Primary outcome:

Efficacy of 16 weeks of ISIS 304801 as compared to placebo (between group comparison) on the change in log₁₀ fasting triglycerides (TG).

4.2.2 Secondary outcomes:

Efficacy of 16 weeks of ISIS 304801 as compared to placebo (between group comparison) on:

Lipids

- Percent change in fasting TG
- Absolute change in fasting TG
- Change in lipolysis rate measured using stable isotope tracers
- Change from baseline in liver volume and hepatic steatosis (as assessed by magnetic resonance imaging [MRI] and magnetic resonance spectroscopy [MRS])
- Lipoprotein lipase activity

Glycemic

- Change in total body insulin sensitivity using the hyperinsulinemic euglycemic clamp
- Change in hepatic glucose production and hepatic insulin sensitivity using stable isotope tracers in combination with the hyperinsulinemic euglycemic clamp
- Change in hemoglobin A1c (HbA1c)
- Change in fasting plasma glucose

Safety

- Safety and tolerability of ISIS 304801
- Prospectively adjudicated acute pancreatitis events (Atlanta classification) and Major Adverse Cardiovascular Events (MACE)

Pharmacokinetic

- Plasma ISIS 304801 level

4.2.3 Tertiary/Exploratory outcomes:

Efficacy of 16 weeks and 16 months of ISIS 304801 as compared to immediately prior to treatment (pre-post within subject comparison) on:

Lipids

- Change in other fasting lipid measurements: high-density lipoprotein cholesterol (HDL-C), low-density lipoprotein cholesterol (LDL-C), total cholesterol (TChol), very low-density lipoprotein cholesterol VLDL-C, non-HDL-C, apolipoprotein B (apoB), apolipoprotein B-48 (apoB48), apolipoprotein A1 (apoA1), apolipoprotein CIII (apoC-III; total, chylomicron, VLDL, LDL and HDL), and free fatty acids
- Change in lipoprotein particle size/number by nuclear magnetic resonance (NMR)
- Triglyceride (and other lipid particle) clearance following mixed meal testing

Glycemic

- Change in 24-h glucose (using 7-point plasma blood glucose)
- Change in fasting and area under the curve for insulin and C-peptide during mixed meal testing
- Reduction in insulin use

Adipose tissue

- Change in skinfold thickness and dual-energy X-ray absorptiometry (DEXA)
- Change in abdominal VAT and SAT volumes
- Change in adiponectin and leptin
- Change in body weight and waist circumference

Cardiovascular

- Carotid intima-media thickness (by ultrasound)
- Coronary artery wall thickness and diameter change after hand-grip exercise (by MRI)

Patient Reported Outcomes

- Change in Quality of Life (EQ-5D, SF36)
- Change in hunger visual analog scale
- Change in pain

Other

- Change in testosterone
- Metabolomics
- Liver histopathology

Efficacy of 16 weeks of ISIS 304801 as compared to placebo (between subject comparison) on the primary and secondary outcomes, above.

5. Statistical Considerations

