5.2 Statistical Methods for Data Analysis

Descriptive statistics such as mean and standard deviation (or median and interquartile range) will be used to summarize data in raw scale or change from baseline per visit.

The primary outcome, change in log₁₀ TG at Week 16 from baseline, and continuous secondary outcomes will be compared between ISIS 304801 and placebo groups using either two-sample t-test or Wilcoxon rank sum test as appropriate based on change from Baseline at Week 16. Changes from baseline based on tertiary/exploratory outcomes as well as change on log₁₀ TG at Week 16 will be examined using either one-sample t-test or Wilcoxon signed rank test as appropriate.

Repeated measures analysis of covariance using linear mixed models will be conducted in order to investigate trends on selected response variables and to compare active and placebo group while possible covariates are taken into account. There are three possible covariates: (1) Baseline level of the outcome of interest, (2) Baseline level of ApoCIII, and (3) Change in ApoCIII before and after the 16 week active drug intervention.

Inclusion of covariates will be checked using linear mixed models by checking Akaike Information Criteria (AIC) with inclusion of one covariate at a time

Analyses will include all available data even if patients do not adhere to their assigned treatments. Additional analyses will examine the effect of adherence to study results. We will also investigate the effect of missing data on the results using standard methods for missing data.

A p-value of 0.05 or less is considered significant.

6. Experimental Plan

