6.4.2 Detailed Metabolic Phenotyping

1. **Anthropometric measurements:** Physical exams and vital signs will be performed as indicated in the Schedule of Procedures (Appendix A). Height will be measured in the early morning on the first full day of the first inpatient visit. Vital signs will include weight, blood pressure, pulse rate, respiratory rate and body temperature. Blood pressure and pulse rate will be recorded after the patient has been in a sitting position for at least 5 minutes. Systolic and diastolic blood pressure should always be measured on the same arm (preferentially on the left arm). Waist circumference will be measured at the iliac crest in triplicate to the nearest tenth of a cm using a stretch-less, tension-sensitive tape measure at the times indicated in the Schedule of Procedures (Appendix A). Skinfold measurements will be obtained in triplicate to the nearest mm using regularly calibrated Lange skinfold calipers at the times indicated in the Schedule of Procedures (Appendix A).

2. Fasting labs: Blood samples will be obtained following a minimum 8 hour fast for analytes described in Appendix A. Ideally the morning blood draw will be coordinated so that it will be collected 10 hours after the evening meal. Additional serum and plasma samples will be stored for future analysis.
3. DEXA scan for total body composition: DEXA scans will be conducted prior to administration of the first dose of study drug and repeated after the 16 week placebo controlled period, and again after 16 weeks of open-label drug in those previously assigned to placebo. A DEXA scan (iDXA, GE Healthcare, Madison WI) will be performed to determine total and regional body fat and lean soft tissue masses, bone mineral content and density. DEXA produces photons at two different energy levels, 40 and 70 KeV. The photons pass through tissues and attenuate at rates related to elemental composition. Bone mineral, with highly attenuating calcium and phosphorous, is readily distinguished from soft tissues. The different elemental profiles of fat and bone-mineral free lean components allows for the analysis of soft tissue fat content, so that bone mineral, fat, and bone mineral fat-free lean components may be resolved.

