Appendix A: Schedule of Study Procedures

Study Period	Pre-Screen	Screen	Double-Blind					Open Label Extension										Post Treatment		
Study Week (from enrollment)	-8 to -2	-1	1	4	8	12	13	16	20	24	28	32	36	40	48	56	64	68	74	80
Study week (from start of open label extension)									4	8	12	16	20	24	32	40	48	52		
Inpatient Visits		x						x				x						x		x
Home Nurse visit**				x	x	x	x		x	x	x		x	x	x	x	x		x	
Telephone contact				x	x	x	x		x	x	x		x	x	x	x	x		x	
Inclusion/Exclusion Criteria	x	x																		
Medical History Review	x	x																		
Vital Signs/Weight/Height		x						x				x						x		x
Physical Exam		x						x				x						x		x
Waist Circumference		x						x				x						x		x
Skinfold measurements		x																		
DEXA Scan			x					x				x						x		
Glucose and Lipid Turnover			x					x				x						x		x
Euglycemic Hyperinsulinemic Clamp			x					x				x						x		x
Mixed Meal Test			x					x				x						x		x
Urinalysis & protein:creatinine ratio		x		x	x		x	x	x	x	x	x		x		x		x		x
Liver Biopsy			x															x		
MRI/MRS liver/heart			x					x				x						x		
Carotid intima-media thickness			x					x				x						x		
12-Lead EKG		x						x				x ¹						x		

7-point plasma glucose			X					X				X						X		X	
Weekly Study Drug SQ Injection			X	X	X	X	X	X	X	X	X	X	X	X	X	X	X	X	X		
Glucometer Dispensation/Training			X																		
Hunger Diary			X					X				X						X		X	
Widespread Pain Diary			X					X				X						X		X	
Quality of Life Assessments			X					X				X						X		X	
Review SMPG and Insulin Dose			X	X	X	X	X	X	X	X	X	X	X	X	X	X	X	X	X	X	X
Diet/Alcohol Counseling	---X---		X	X	X	X	X	X	X	X	X	X	X	X	X	X	X	X	X	X	X
Adverse Events			X	X	X	X	X	X	X	X	X	X	X	X	X	X	X	X	X	X	X
Concomitant Medication Review	X		X	X	X	X	X	X	X	X	X	X	X	X	X	X	X	X	X	X	X

¹ Patients previously treated with placebo, only

² One sample obtained on each of two consecutive days

³ Sampling schedule can be found in Appendix C.
 Unless specified, otherwise, PK and Antibodies will be collected predose.
 PK and immunogenicity testing does not need to be collected fasting.

* Platelets will be assessed every week

** Home Health Nurse Visits (or lab draw by local lab facility when needed) will take place every week unless patient will be at NIH for in-person visit.

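### Change in skinfold thickness is a listed exploratory outcome at 16 weeks and 16 months, but Appendix A schedules skinfolds only at screening

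*Combined protocol and SAP*

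**What the plan says.** Section 4.2.3 puts "Change in skinfold thickness and dual-energy X-ray absorptiometry (DEXA") under its adipose tissue heading. The contrast for that whole list is "Efficacy of 16 weeks and 16 months of ISIS 304801 as compared to immediately prior to treatment (pre-post within subject comparison) on" each item. Section 5.2 says how such outcomes are analysed: "Changes from baseline based on tertiary/exploratory outcomes" go to a one-sample t-test or a Wilcoxon signed rank test.

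Section 6.4.2 item 1 gives the method and hands the timing to the schedule: "Skinfold measurements will be obtained in triplicate to the nearest mm using regularly calibrated Lange skinfold calipers at the times indicated" in Appendix A. It names no visits of its own.

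In Appendix A, the row "Skinfold measurements" carries one mark, in the Screen (Week -1) column. Section 6.3.3 explains that measurement: skinfolds are part of the physical examination used to establish eligibility, and inclusion criterion 5 sets an anterior-thigh caliper cut-off.

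DEXA, the other half of the same outcome item, is treated differently. Section 6.4.2 item 3 states that "DEXA scans will be conducted prior to administration of the first dose of study drug and repeated after the 16 week placebo controlled period", with a further scan after 16 weeks of open-label drug in those who began on placebo.

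**The concern.** A change score needs a value before drug and a value on drug in the same subject. The outcome list and the analysis section both assume such pairs. The schedule, the only place that sets the timing, does not produce them. A site that follows Appendix A would measure skinfolds once, for eligibility, and the planned test for this outcome would have no data.

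What is at stake is one listed exploratory outcome that would go unreported or be filled in from unscheduled readings. A caliper reading not taken at a visit cannot be reconstructed afterwards.

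**Working it through.** The plan gives no figure to reproduce here. The check sets the outcome definition against the schedule.

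**1. What the outcome needs.** For each subject, change = skinfold on drug − skinfold immediately before drug. A one-sample test uses only subjects with both values.

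**2. Which visits would supply those values.** The blinded phase lasts 16 weeks and the open-label extension 52 weeks, so Week 68 = 16 + 52.
- Drug-first subjects: before drug = Screen; 16 weeks on drug = Week 16; 16 months on drug (4 + 12 months) = Week 68.
- Placebo-first subjects: before drug = Week 16; 16 weeks on drug = Week 16 + 16 = Week 32. By Week 68 they have had 68 − 16 = 52 weeks of drug, so the main schedule reaches 16 months of drug only in the drug-first group.

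**3. What Appendix A schedules.** Marks counted by row against its 20 visit columns:

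| Row | Before first dose | Weeks marked after first dose | Post-baseline marks |
|---|---|---|---|
| Skinfold measurements | Screen | none | 0 |
| Waist circumference | Screen | 16, 32, 68, 80 | 4 |
| DEXA scan | Week 1 | 16, 32, 68 | 3 |
| MRI/MRS | Week 1 | 16, 32, 68 | 3 |

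**4. Pairs obtained.**
- Drug-first: the before-drug value is present, but both follow-up values (Weeks 16 and 68) are absent. Pairs = 0.
- Placebo-first: the Week 16 value just before active drug and the Week 32 value are both absent. Pairs = 0.
- Against the goal of 10 completers in Section 5.1, the schedule yields 0 of 10 pairs at the stated time points.

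**5. Is the row merely damaged in the text?** This is unlikely. The rows directly above (physical exam, waist circumference) and directly below (DEXA) keep their follow-up marks in the right columns. The DEXA marks also agree with the scan times written out in Section 6.4.2.

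**6. Other routes to a later skinfold.** Section 6.3.7 lets patients have any Section 6.4 test except liver biopsy at the visit ending the additional 12-month open-label period. That evaluation is optional, is open only to patients whose triglycerides improved by at least 50% and who chose to continue, and falls after both stated time points.

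**The case against.** Four points can be made on the other side.

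- **Skinfolds may come with every physical examination.** Section 6.3.3 describes the examination as including them, and physical exams recur at Weeks 16, 32, 68 and 80. But that wording belongs to the list of eligibility tests at the initial visit, and Appendix A gives skinfolds a row separate from physical exam. At most, this shows that the text could be read in two ways.
- **The extracted schedule is incomplete.** Some rows the text refers to, such as echocardiogram and troponin, do not appear, and some footnotes have lost their anchors. The skinfold row should be checked against the source table, although its neighbours give no sign of a lost mark.
- **Little is lost.** This stands. DEXA gives total and regional fat, and abdominal visceral and subcutaneous fat volumes are a separate outcome measured by MRI. The hypotheses concern triglycerides, glucose metabolism, hepatic steatosis and cardiovascular risk markers, not restoration of subcutaneous fat. Skinfold has no entry in the power table.
- **The study was already under way.** Section 7.14 refers to 5 enrolled patients who had been treated, so a change to the schedule may help only visits still to come. This also stands.

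A reader might go further and infer that a comparison of drug with placebo is lost. The documents do not support that. Section 4.2.3 defines its tertiary outcomes as within-subject and reserves the placebo comparison for the primary and secondary outcomes, and Section 5.2 assigns tertiary outcomes one-sample tests. The mixed model in Section 5.2 does compare groups on selected variables, but nothing names skinfold as one of them. A reader might also infer that no skinfold change could ever be computed. Section 6.3.7 leaves an optional late measurement open, so that is too strong as well.

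**Conclusion.** The plan contradicts itself on this outcome and is wrong as written. Section 4.2.3 calls for within-subject skinfold change at 16 weeks and 16 months, while the scheduled assessments give no pair at either point. Placebo-first subjects lack the pre-drug reading as well as the follow-up.

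The consequence is minor. One half of one exploratory item cannot be reported from scheduled data; the primary and secondary analyses do not depend on it, and the DEXA and MRI measures of body fat are intact. The conclusion assumes that the single mark in the Appendix A row is genuine and that sites follow that row rather than reading skinfolds into each physical examination.

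**What to change.** Choose one of two edits.

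1. **Keep the outcome.** In Appendix A, mark skinfold measurements at Weeks 16, 32 and 68, alongside waist circumference and DEXA, using the triplicate caliper method in Section 6.4.2. Week 16 supplies the 16-week value for drug-first subjects and the pre-drug value for placebo-first subjects. Week 32 supplies the 16-week value for placebo-first subjects. Week 68 supplies the 16-month value for drug-first subjects.
2. **Drop the outcome.** Delete skinfold change from Section 4.2.3, keep the screening measurement for eligibility, and rely on DEXA and MRI for change in body fat.

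The first edit costs one schedule row and a few minutes of caliper work at inpatient visits that already take place; it adds no visit or equipment. The second costs one phrase. If the first is adopted with some visits already past, report how many subjects contribute a pair at each time point.

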5.1 Sample Size Justification

The primary outcome variable is the change in log₁₀ fasting triglycerides from before treatment to 16 weeks of active drug treatment compared to placebo groups.

Preliminary data are available for 28 patients treated with ISIS 304801 and 24 treated with placebo. For the ISIS 304801 group, these data show a difference from baseline to follow-up of -423 (SD 400, 95% CI -578 to -268) mg/dL and -0.485 (SD 0.221, 95% CI -0.57 to -0.40) log₁₀ mg/dL. Converting the difference in log₁₀ mg/dL to a percent change [$100 \times (10^{-0.485} - 1)$] results in a percent change of -67% (95% CI -73% to -60%). For the placebo group, the absolute change is -12 (SD 406, 95% CI -12 to 184) mg/dL and -0.011 (SD 0.224, 95% CI -0.105 to 0.084) log₁₀ mg/dL. The percent change for the placebo group is -3% (95% CI -21% to 21%).

For comparison of placebo and ISIS 304801 we have chosen a SD of 0.25 log₁₀ mg/dL and a difference of 0.50 log₁₀ mg/dL. A trial with 5 patients in each group has 79% power to detect a difference of 0.50 log₁₀ mg/dL triglycerides in the change from baseline to follow-up between the ISIS and placebo groups, assuming a SD of 0.25 log₁₀ mg/dL and a two-sided significance level of 0.05.

Where preliminary data were available, sample size calculations were performed for secondary and tertiary study outcomes in addition to the primary outcome. The preliminary data and power estimates for a sample size of 10 subjects (using one-sample t-test for off versus on drug comparisons) are summarized in the table below. Based on these calculations, the study should be adequately powered to detect differences in total body insulin sensitivity, hepatic insulin sensitivity, fasting glucose, apoC-III serum level, HDL-C, VLDL-C, and apolipoprotein B48.

Based on these calculations, we plan to enroll a maximum of 20 patients, with a goal of 10 patients completing the study (defined as completing 16 weeks of active drug treatment). The accrual ceiling of 20 is planned because subjects will consent to the study prior to screening, thus we are accounting for up to 10 screen failures in the accrual ceiling.

	Outcome	Model	Treatment	Treat- ment Duration	Mean of Δ on-off drug (SD)	Power
Primary outcome	Absolute change log[serum triglycerides] (mg/dL)	High TG +/- diabetes and/or fibrate	ApoCIII ASO 300 mg/wk	16 wk	-0.48 (0.22)	>0.95
	% change serum triglycerides (%)	High TG +/- diabetes and/or fibrate	ApoCIII ASO 300 mg/wk	16 wk	-63 (20)	>0.95
	Absolute change serum triglycerides (mg/dL)	High TG +/- diabetes and/or fibrate	ApoCIII ASO 300 mg/wk	16 wk	-423 (400)	0.85
Secondary outcomes	Hemoglobin A1C (%)	Type 2 diabetes	ApoCIII ASO 300 mg/wk	16 wk	-0.2 (0.36)	0.35
	Total body insulin sensitivity (glucose infusion rate during clamp, mg*kg ⁻¹ *min ⁻¹)	Type 2 diabetes	ApoCIII ASO 300 mg/wk	16 wk	1.6 (1.2)	>0.95
	Hepatic insulin sensitivity (% suppression of endogenous glucose production during clamp)	Type 2 diabetes	ApoCIII ASO 300 mg/wk	16 wk	11.0 (5.6)	>0.95
	Fasting plasma glucose (mg/dL)	Type 2 diabetes	ApoCIII ASO 300 mg/wk	16 wk	-35 (36)	0.78

	ApoCIII serum level (mg/dL)	High TG +/- diabetes and/or fibrate	ApoCIII ASO 300 mg/wk	16 wk	-15.3 (7.5)	>0.95
	HDL-C (mg/dL)	High TG +/- diabetes and/or fibrate	ApoCIII ASO 300 mg/wk	16 wk	13.3 (10.1)	>0.95
Tertiary Outcomes	LDL-C (mg/dL)	High TG +/- diabetes and/or fibrate	ApoCIII ASO 300 mg/wk	16 wk	31.3 (47.3)	0.46
	Total Cholesterol (mg/dL)	High TG +/- diabetes and/or fibrate	ApoCIII ASO 300 mg/wk	16 wk	-32 (72)	0.24
	VLDL-C (mg/dL)	High TG +/- diabetes and/or fibrate	ApoCIII ASO 300 mg/wk	16 wk	-77 (60)	0.95
	non-HDL-C (mg/dL)	High TG +/- diabetes and/or fibrate	ApoCIII ASO 300 mg/wk	16 wk	-46 (74)	0.42
	Apolipoprotein B (mg/dL)	High TG +/- diabetes and/or fibrate	ApoCIII ASO 300 mg/wk	16 wk	-5.8 (30)	0.09
	Apolipoprotein B-48 (mg/dL)	High TG +/- diabetes and/or fibrate	ApoCIII ASO 300 mg/wk	16 wk	-0.44 (0.43)	0.82
	Free Fatty Acids (uEq/L)	Familial chylomicron-emia	ApoCIII ASO 300 mg/wk	16 wk	-0.40 (0.44)	0.73
	Body Weight (kg)	High TG +/- diabetes and/or fibrate	ApoCIII ASO 300 mg/wk	16 wk	-0.87 (1.69)	0.30

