The purpose of this study is to determine if apoC-III reduction using an ASO to apoC-III (ISIS 304801) will reduce triglycerides and improve insulin resistance, diabetes, and hepatic steatosis in patients with lipodystrophy. The primary hypothesis to be tested is:

1. ISIS 304801 will reduce log₁₀ fasting serum triglycerides.

Secondary and tertiary hypotheses to be tested are:

2. ISIS 304801 will improve glucose metabolism by improving insulin resistance.
3. ISIS 304801 will reduce hepatic steatosis.
4. ISIS 304801 will improve cardiovascular risk markers.

We will also explore the mechanism of action of apoC-III ASO by studying lipoprotein lipase activity and lipoprotein particle distribution.

Methods

This study will enroll up to 20 patients with partial lipodystrophy with a goal of 10 study completers. The study will be conducted in two phases. The first is a 16-week, randomized, double-blind, placebo-controlled design. Subjects will be treated with ISIS 304801 at a target dose of 300 mg per week or placebo. Following this phase, all subjects will enter a 12 month open-label extension in which they will receive active drug. Patients who experience benefit (triglyceride lowering $\geq 50\%$) may receive an additional 12 months of open-label drug (up to 24 months, total). Measurement of the primary outcome (serum triglycerides) and key secondary outcomes will be performed at baseline prior to the intervention, after 16 weeks (primary and secondary outcomes) of blinded drug or placebo, and after an additional 4 months of active drug in subjects initially randomized to placebo.

STUDY GLOSSARY

Abbreviation	Definition
2'-MOE	2'-O-(2-methoxyethyl)
AE	adverse event
ALT	alanine aminotransferase (SGPT)
ANA	antinuclear antibody
apoA1	apolipoprotein A1
apoB	apolipoprotein B
apoC-III	apolipoprotein C-III
apoE	apolipoprotein E
aPTT	activated partial thromboplastin time
ASO	antisense oligonucleotide
AST	aspartate aminotransferase (SGOT)
BMI	body mass index
BP	blood pressure
DEXA	dual-energy X-ray absorptiometry
DSMB	Data and Safety Monitoring Board
EKG	electrocardiogram
eCRF	electronic Case Report Form
FPG	fasting plasma glucose
FPL	familial partial lipodystrophy
FSH	follicle-stimulating hormone
GCP	Good Clinical Practice
HBsAg	hepatitis B surface antigen
HBV	Hepatitis B virus
HbA1C	Hemoglobin A1C
HCV	hepatitis C virus
HDL-C	high-density lipoprotein cholesterol
hERG	human ether-a-go-go
HIV	human immunodeficiency virus

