1.2 Secondary/Tertiary Objectives

To evaluate the efficacy of 16 weeks of ISIS 304801 as compared to placebo (between group comparison) on additional lipid, glycemic, hepatic, and cardiovascular parameters (see Outcome Measures), as well as safety and tolerability of ISIS 304801. In addition, the effects of ISIS 304801 (defined as tertiary outcomes) as compared to immediately prior to treatment (pre-post within subject comparison) for 16 weeks on these outcomes will be evaluated.

2. Introduction

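### Section 5.1 calls the study adequately powered for total body insulin sensitivity and fasting glucose on a one-sample test in 10 subjects, but their designated secondary test is 5 versus 5 against placebo, with power of about 0.46 and 0.27

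*Combined protocol and SAP*

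**What the plan says.** Section 5.1 describes its table as giving "power estimates for a sample size of 10 subjects (using one-sample t-test for off versus on drug comparisons"), and then draws a conclusion about the study as a whole: "Based on these calculations, the study should be adequately powered to detect differences in total body insulin sensitivity, hepatic insulin sensitivity, fasting glucose". The table lists mean change (SD) and power of 1.6 (1.2) mg/kg/min and >0.95 for total body insulin sensitivity, and -35 (36) mg/dL and 0.78 for fasting plasma glucose. The only between-group power in 5.1 is 79% for log10 triglycerides with 5 patients per group.

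Section 4.2.2 introduces the secondary outcomes as "Efficacy of 16 weeks of ISIS 304801 as compared to placebo (between group comparison) on" a list that includes "Change in total body insulin sensitivity using the hyperinsulinemic euglycemic clamp" and the change in fasting plasma glucose. Section 5.2 says that "continuous secondary outcomes will be compared between ISIS 304801 and placebo groups using either two-sample t-test or Wilcoxon rank sum test as appropriate", on change from baseline at Week 16.

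The within-subject comparison is also planned. Section 1.2 describes "the effects of ISIS 304801 (defined as tertiary outcomes) as compared to immediately prior to treatment (pre-post within subject comparison"). The Precis has key secondary outcomes measured again "after an additional 4 months of active drug in subjects initially randomized to placebo", so an on/off-drug comparison in all 10 completers is feasible.

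**The concern.** The power figures and the designated secondary test belong to different comparisons. A one-sample test in 10 subjects uses every completer and carries no placebo-arm variance. A two-sample test with 5 per group has half as many patients on drug and adds the placebo arm's variance. The same mean and SD therefore give much lower power.

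The placebo comparison is the one with a concurrent control, and better glucose metabolism through improved insulin resistance is the second hypothesis in the Precis. A reader who takes the adequacy statement to cover that comparison could read a non-significant result as evidence of no glycemic effect, when the test would probably miss an effect of the assumed size.

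The labels make the mismatch harder to see. Section 1.2 calls the pre-post comparison tertiary, 4.1 puts secondary and tertiary outcomes together under within-subject comparisons, and 4.2.3 lists the placebo comparison of the primary and secondary outcomes again under tertiary.

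The point is limited to these two outcomes. ApoC-III, HDL-C, VLDL-C and apoB-48, also named as adequately powered, are pre-post outcomes in 4.2.3, so the one-sample basis fits them. Hepatic insulin sensitivity is treated in the working.

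**Working it through.** **Inputs.** Means, SDs and stated powers come from the 5.1 table. Five per group follows from 10 completers (5.1) and 1:1 allocation (4.1). Two-sided 0.05 is stated for the primary outcome and reproduces the table. The documents give no placebo change or SD for the two glycemic outcomes, so those are assumptions.

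**Formulas.** With d = mean/SD, power comes from the noncentral t distribution:

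- one-sample, n = 10: df 9, noncentrality d × √10;
- two-sample, 5 per group: df 8, noncentrality d / √(2/5), critical value 2.306.

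**Reproducing the plan.**

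- Primary: d = 0.50/0.25 = 2.0, noncentrality 3.162, power 0.791 (stated 79%).
- Insulin sensitivity, one-sample: d = 1.6/1.2 = 1.333, noncentrality 4.216, power 0.962 (stated >0.95).
- Fasting glucose, one-sample: d = 35/36 = 0.972, noncentrality 3.074, power 0.781 (stated 0.78).

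**The designated secondary test, 5 versus 5, zero placebo change, equal SDs.**

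- Insulin sensitivity: noncentrality 1.333/√0.4 = 2.108, power 0.458.
- Fasting glucose: noncentrality 0.972/√0.4 = 1.537, power 0.273.
- Hepatic insulin sensitivity, for comparison: d = 11.0/5.6 = 1.964, power 0.776. This is close to the 79% accepted for the primary outcome, so it is left out of the claim.

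The rank sum alternative allowed in 5.2 does worse under the same normal model: about 0.34 and 0.20 by simulation.

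**Range over the unknown placebo inputs** (pooled t; unequal SDs by simulation):

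| Assumption | Insulin sensitivity | Fasting glucose |
|---|---|---|
| Placebo SD 1.25 × drug SD, no change | 0.38 | 0.23 |
| Equal SDs, no change | 0.46 | 0.27 |
| Placebo SD 0.5 × drug SD, no change | 0.65 | 0.41 |
| Placebo SD near zero, no change | 0.74 | 0.51 |
| Equal SDs, placebo moves 25% of drug effect, same direction | 0.29 | 0.17 |
| Equal SDs, placebo moves 25% of drug effect, opposite direction | 0.64 | 0.39 |

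**Detectable difference at 80% power.** 5 versus 5: 2.02 SD, which is 2.4 mg/kg/min (2.024 × 1.2) and 73 mg/dL (2.024 × 36). One-sample, n = 10: 1.00 SD. At equal SDs, 80% power would require placebo patients to worsen by 2.024 × 1.2 − 1.6 = 0.83 mg/kg/min (52% of the drug effect) or 2.024 × 36 − 35 = 38 mg/dL (108% of it). With no placebo change, 80% power would take about 10 and 18 patients per group.

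**Cross-check where 5.1 does give placebo data.** Absolute triglyceride change is a between-group secondary outcome in 4.2.2. It is not among the outcomes called adequately powered and serves only to size the gap. The drug change is -423 (SD 400); for placebo 5.1 says "For the placebo group, the absolute change is -12 (SD 406, 95% CI -12 to 184) mg/dL". The pooled SD is √((400² + 406²)/2) = 403 and d = 411/403 = 1.020, so 5-versus-5 power is 0.30, against 0.85 in the table. The printed placebo interval does not fit a mean of -12. With n = 24 the half-width is 2.069 × 406/√24 = 171, so a mean of +12 would give -159 to 183, close to the printed upper limit. Using +12, d = 435/403 = 1.079 and power is 0.32.

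**The case against.** The strongest reply is that nothing is hidden. The sentence immediately before the conclusion names the one-sample test, the conclusion refers back to those calculations, and the table column is headed as an on-minus-off-drug change. Read in place, the adequacy statement is about the on/off comparison, which is planned and feasible and whose stated power is right. This stands as a description of the basis. It does not rescue the conclusion, which is drawn for the study without restriction and covers outcomes whose designated secondary test is a different one.

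The documents are also not uniform on the labels. Section 4.1 groups secondary outcomes with within-subject comparisons, and 4.2.3 repeats the placebo comparison under tertiary. That is fair, but 4.2.2 and 5.2 are explicit about the between-group test. The loose labels need reconciling; they do not support the power claim.

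The placebo inputs are unknown, so 0.46 and 0.27 are conditional figures. This stands, and they should be quoted with their range.

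Finally, 5.2 also plans mixed models that may adjust for baseline. With one covariate (df 7, equal SDs, zero placebo change), 80% power would need a correlation between baseline and change of about 0.76 for insulin sensitivity and 0.88 for fasting glucose. The documents give no such correlations, and adjustment is conditional on a model-selection step, so it cannot be counted on.

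The consequence is one of interpretation. The sample size is set by the primary outcome, and no decision rule depends on these two outcomes.

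**Conclusion.** The concern holds. For total body insulin sensitivity and fasting plasma glucose, the adequacy statement in 5.1 is true of the within-subject comparison in 10 subjects and is not supported for the secondary test laid down in 4.2.2 and 5.2. Power for that test is about 0.46 and 0.27, against >0.95 and 0.78 in the table, given the table's means and SDs, no placebo change and equal SDs. No placebo SD brings either outcome to 0.80 while the placebo change is zero. Adequate power at equal SDs would require substantial worsening on placebo. The table's arithmetic and the primary outcome's 79% are correct. This should be fixed, because it misstates a property of the plan that readers will use to interpret a null result.

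**What to change.** 1. In 5.1, state that the power column and the adequacy sentence apply only to the within-subject, one-sample comparison in 10 subjects.
2. Add the 5-versus-5 power for the between-group secondary outcomes, or the detectable difference (about 2.02 SD at 80% power), with the assumed placebo change and SD and a range.
3. Say that, under those assumptions, the placebo comparisons of total body insulin sensitivity and fasting plasma glucose are not adequately powered.
4. Make the labels agree across 1.2, 4.1, 4.2.2 and 4.2.3, so that each outcome's within-subject and between-group comparison has one stated tier.

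The cost is wording in those sections and one added sentence or table column. The stated power becomes less favourable. No patients, visits or data are added.
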